Total body muscle mass will be assessed directly by the D₃-creatine dilution method (27). Low muscle mass measured by this method has been associated with slower walking speed, lower SPPB score, and more falls in older men (27). The D₃-creatine dilution method involves a participant ingesting a capsule containing the 60-mg dose of stable isotope-labeled creatine (D₃-creatine), and then providing a fasting morning urine sample 72–144 hours (3–6 days) later. To minimize variability in this muscle mass measurement, participants will be asked not to eat foods containing creatine or creatinine (animal products) after their mid-day meal on the day prior to these urine collections on visits 0 and 12 months. A handout will be provided to guide participants in what they should and should not eat on these two occasions. Urine D₃-creatinine, unlabeled creatinine, and creatine are measured using high performance liquid chromatography and tandem mass spectroscopy; these measures are then included in an algorithm to determine total body creatine pool size and thus skeletal muscle mass (39). The doses will be prepared by Greenpark Pharmaceuticals in Houston, TX. The urine samples will be de-identified and sent to [name] laboratory at U.C. Berkeley for analysis. [name] will be blinded to treatment group and sequence (baseline, 12 mo) during the analyses.

Biochemical measurements

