The Bioinformatics Specialist, [name], will create the one to one randomization allocation for this study using a block randomization stratified by sex. Due to the small sample size, a block size of 4 will be used. At enrollment, subjects will be randomized by a research coordinator using the randomization module in REDCap. When the subject comes for the baseline visit, a research coordinator will notify the TMC pharmacy of the treatment assignment (group A or group B). A research coordinator will pick up the pill bottle from the Pharmacy and give it to the subject. With the exception of the bioinformatics specialist, the study statistician,

and the pharmacist, all study personnel will be blinded to treatment assignment. In the event of an SAE and upon recommendation of the study physician, the bioinformatics specialist will inform the participant's primary care physician of the treatment assignment. The study physician will remain blinded.

H. Data management

Data collected during this single-site study will not leave the site. All data will be entered into electronic data capture (EDC) forms built in REDCap. Primary data records include: EDC forms completed by the research coordinator during subject interviews and physical measurements, electronic database files generated directly by the DXA bone scanning equipment, and electronic database files of biochemical screening tests generated by the Nutrition Evaluation Laboratory.

All electronic data forms will utilize data entry validation for data types and data ranges to minimize potential for error and will undergo monthly data quality checks by a member of the Biostatistics and Data Management Core Unit at the HNRCA to ensure data quality.

The study database and all source data will be maintained on the HNRCA REDCap server for a minimum of 10 years post study completion per the HNRCA data retention policy. Duplicate copies of these data will be maintained on the HNRCA disaster recovery server as well as the Bone Metabolism Laboratory network storage.

Electronic DXA data files are generated by the DXA scanner located in the Bone Metabolism Laboratory. Biochemical data are manually entered by staff of the Nutrition Evaluation Laboratory and transferred into REDCap. Original paper copies of biochemical assay results are kept in the Nutrition Evaluation Laboratory until and beyond the end of all study activity.

I. Study power

Aim 1: Muscle mass by D₃-creatine dilution –

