The recently published study in Duchowny et al. (13), looked at change in muscle mass assessed by the D₃-creatine dilution method. Table 2 in the paper reports estimated mean change in D₃-Cr muscle mass over 1.6 years in 40 men (mean age 83 years), duplicated below.

Table Simple linear change

variable	mean	SD
D ₃ -Cr muscle mass (kg)	-1.42	1.84
weight (kg)	-0.63	2.92
D ₃ -Cr muscle mass/weight	-0.02	0.02

We will use SD=1.84 to represent standard deviation of change for D₃-Cr muscle mass (kg). Additionally, -1.42 kg over 1.6 years is equivalent to -0.89 kg per year (what we might expect in the placebo group).

A difference (anamorelin vs placebo) in 3 month change of 0.57 kg and 0.83 kg in appendicular LBM was observed in the two replicate studies (26). Assuming a linear rate of change, we can expect a change in muscle mass of 2.28-3.32 in 12 months. A linear rate of change is reasonable since in the safety extension of these original trials, continued response in weight change during the trial was observed out to 6 months (29).

Twelve participants per group are required to have a minimal detectable difference below 2.28 kg between anamorelin and placebo.

Aim 2: P1NP- The bone formation marker, P1NP, is the key secondary endpoint. Between-subject variation in 84-day change in P1NP was estimated from our previous clinical trial in 244 men and women age 50 and older (42). Standard deviation of 84-day change in P1NP was 0.267 nmol/L in all three treatment groups (42). With N=12 completers per group, statistical power is 82% to detect a difference of 0.32 nmol/L between placebo

and treatment, which is a 25% change. P1NP has not been measured in anamorelin treated subjects, but detecting a 25% group difference from placebo is clinically meaningful and it is plausible given that another ghrelin receptor agonist, MK-677, induced a 29% increase in another bone formation marker, serum osteocalcin, over a 2-week period (30).

J. Data analysis

Baseline subject characteristics will be tabulated and summary statistics reported for all measured outcomes at each time point.

Primary aim – The change in muscle mass over 12 months will be compared between the intervention and control groups with a two-sample Student's t-test. Should the groups be imbalanced in factors known to influence muscle mass (i.e., sex, age, HABC-PPB, physical activity level, and dietary protein intake), we will adjust for those confounders within an ANCOVA model.

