Secondary aims - With 4 measurements (baseline, 2, 6, and 12 months), we will test whether the change over time is linear with use of linear models with random effects. The observed pattern of change in ALM over time will give an indication of the potential long-term benefit (or lack thereof) of anamorelin treatment. A significance level of 0.05 will be used.

The findings from secondary (and exploratory) analyses will be used for hypothesis generation, rather than to draw conclusions.

Exploratory aims – Exploratory outcomes will be analyzed as described above. For those with more than two measurements, the pattern of change will be analyzed as described above for ALM.

The primary analyses will follow intention-to-treat principles. The intent to treat population will include all subjects who had 1 or more visits after visit 0 (baseline). We will also perform per protocol analyses, in which subjects who develop clinical conditions during the study that influence the study outcomes (i.e., started treatment on an osteoporosis drug or glucocorticoids) or with selected protocol deviations will be excluded. Data will be diagnosed to evaluate validity of model assumptions. Assumptions of normality and homoscedasticity will be evaluated in these models and appropriate variable transformations will be applied if needed to satisfy model assumptions. If model assumptions do not hold for the linear mixed models, robust standard errors will be used. An exploratory per-protocol analysis will also be performed.

Safety and tolerability measures will be summarized for each treatment group based on clinical symptoms and circulating levels of glucose and ALT/AST. Adherence will be assessed by intake diary and pill counts.

K. Withdrawal from the study

Participants can go permanently “off study” only for withdrawal of consent, defined as no longer wishing to participate in all aspects of the trial. The PI may also withdraw participants for safety reasons. Participants can be off of study pills (non-adherent) but remain in the study and return for scheduled follow-up visits. Participants who are instructed by their doctor to gain weight during the study will not be withdrawn from the study.

PROTECTION OF HUMAN SUBJECTS

a. Materials and potential risks

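### The primary comparison moves from a t-test to an ANCOVA on an undefined imbalance, and the plan does not say which result is then primary

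*Combined protocol and SAP*

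**What the plan says.** Under Section J (Data analysis, primary aim), change in muscle mass over 12 months "will be compared between the intervention and control groups with a two-sample Student's t-test". The next sentence sets a condition, "Should the groups be imbalanced in factors known to influence muscle mass (i.e., sex, age, HABC-PPB, physical activity level, and dietary protein intake"), and its consequence: "we will adjust for those confounders within an ANCOVA model".

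The list of candidate factors is fixed at five. The section does not give:
- a metric, test or cut-off for imbalance;
- who judges it, and when;
- whether the ANCOVA replaces the t-test or stands beside it.

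The rest of Section J (analysis populations, model assumptions, per-protocol analysis) does not settle these points.

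Three other places bear on this:
- Section G (Randomization) allocates "using a block randomization stratified by sex" and lists those who are not blinded: "With the exception of the bioinformatics specialist, the study statistician" and the pharmacist.
- Section I (Study power) sizes the trial for the unadjusted comparison: "Twelve participants per group are required to have a minimal detectable difference below 2.28 kg between anamorelin and placebo".
- Section F (D₃-creatine) places the muscle-mass urine samples at visits 0 and 12 months, so a baseline value of the primary outcome will exist. It is not among the candidate adjusters.

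**The concern.** The primary p-value comes from one of two models, and an unstated threshold decides which. With 12 completers per arm, chance differences between groups are large. The word can therefore mean anything from a switch in almost every trial to one in about a fifth of them.

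The rule also selects covariates for the wrong reason. After randomisation, an observed difference between arms is chance and says nothing about whether the factor predicts change in muscle mass. Adjusting for an imbalanced factor that is not prognostic costs precision and brings nothing back. Sex, the stratification factor, enters only if it happens to look uneven.

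Finally, with no stated hierarchy, both results could be computed and the more favourable one reported, and the study statistician is not blinded.

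**Working it through.** **Inputs.** From Section I: SD of change 1.84 kg, target difference 2.28 kg, 12 per arm. The 0.05 level is stated in Section J under the secondary aims. Two-sided testing and 80% power for Aim 1 are assumptions, because the documents give neither.

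**1. The plan's own figure.** SE = 1.84 × √(2/12) = 0.751 kg. Noncentrality = 2.28/0.751 = 3.04. The critical t on 22 df is 2.074, so power is 82.7%. The difference detectable with 80% power is 2.20 kg at n = 12 and 2.31 kg at n = 11. Twelve is therefore the smallest n that gives a figure below 2.28 kg, and the plan's statement reproduces for the t-test.

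**2. Chance of a flag.** Take the four continuous factors (age, HABC-PPB, activity, protein intake) as independent.
- Imbalance as p<0.05: 1 − 0.95⁴ = 18.5%.
- Imbalance as p<0.10: 1 − 0.90⁴ = 34.4%.
- More than 0.5 SD: per factor 2[1 − Φ(0.5/√(2/12))] = 0.221, so 1 − 0.779⁴ = 63%.
- More than 0.25 SD: per factor 0.540, so 1 − 0.460⁴ = 96%.

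**3. Consequences, by simulation.** Settings: 12 per arm; pairwise correlation among factors 0 or 0.3; correlation of each factor with change 0 or 0.3 (all assumptions); ANCOVA adjusts for whichever factors are flagged. There were 60,000 replicates per cell, except 30,000 for the power column, which takes the factors as not prognostic.

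| Imbalance means | At least one flagged | Different verdicts at 2.28 kg | Power if the switch is followed | Type I error, better of the two |
|---|---|---|---|---|
| >0.25 SD | 95–96% | 11–14% | about 75.5% | 6.7–7.4% |
| >0.5 SD | 62–66% | 7–10.5% | about 78% | 6.1–6.6% |
| p<0.10 | 32–35% | 4–6% | about 80% | 5.6–5.8% |
| p<0.05 | 17–19% | 3–4% | about 81% | 5.4–5.5% |

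A separate run put the power of the followed switch at about 74–79%, so I quote the wider span of 74–81%. The loss is not universal: if each factor correlates 0.3 with change, the followed switch has about 82–85% power. Any one of these rules, fixed in advance and followed mechanically, has a type I error of 3.3–5.1%.

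**4. A pre-specified ANCOVA on visit-0 muscle mass and sex.** Degrees of freedom fall from 22 to 20 (critical t 2.086). The residual SD is 1.84 × √(1 − R²), where R is the multiple correlation of the two covariates with change. Mean variance inflation is 1.052 if sex is exactly balanced and 1.105 if both covariates vary by chance.
- R = 0: SE = 0.751 × √1.052 = 0.770 to 0.751 × √1.105 = 0.790 kg; power 80% to 78%; detectable difference 2.27 to 2.33 kg.
- R = 0.3: power 84% to 82%.
- R = 0.5: power 90% to 89%.
- Equal to the t-test's 82.7% at R = 0.24 to 0.32.

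**The case against.** The strongest reply is that the sentence has an obvious meaning: if the groups are imbalanced, the ANCOVA replaces the t-test. That is the natural reading, and it leaves an unstated hierarchy rather than two equal candidates. It does not supply the threshold, so the gap remains.

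Several stronger readings are tempting, and the documents do not support them.

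- **That the plan inflates type I error.** A fixed rule does not. Inflation needs both results to be run and the better one kept, which Section J does not describe. Even then it is 5.4–5.8% at the two p-value cut-offs.
- **That the two analyses often disagree.** At a true 2.28 kg they differ in 3–6% of trials at the p-value cut-offs, and in 11–14% only at the loosest one. With no true effect the figures are about 0.8–2.6% and 3.4–5.3%.
- **That blinding offers no protection.** Section F has the D₃-creatine laboratory blinded to group and sequence. The listed factors are measured at visit 0, so imbalance could be judged before outcomes exist. The plan does not require that order.
- **That leaving out sex or baseline muscle mass is an error.** The t-test on change is valid, and omitting a prognostic stratification factor makes it conservative. Including either is an efficiency choice, and the documents give no correlations to settle it.

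Two further items are not counted. Visit-0 values are plainly what the listed factors mean. The clause that "appropriate variable transformations will be applied if needed to satisfy model assumptions" is routine, and its reach to the t-test is unclear.

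It is also fair to say that this is a pilot of 32 people. But Section J confines only the secondary and exploratory findings to hypothesis generation. The primary aim has a stated hypothesis and a power calculation.

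**Conclusion.** The point holds in a limited form: the primary result is not uniquely specified. The trigger has no threshold, and the status of the t-test once the trigger fires is left to inference. The sample size is not in question.

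The firmest consequence is a loss of power, up to about 8 points below 82.7%, if the rule is followed and the listed factors are not prognostic. The risk to type I error is smaller and depends on a choice made after seeing both results. An unblinded statistician could make that choice, but nothing in the plan says that anyone will.

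The flag, disagreement and error rates rest on assumed factor correlations of 0 or 0.3. The power figures rest on Section I's SD of 1.84 kg and on two-sided 0.05. This should be corrected, and wording alone will do it.

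**What to change.** Before unblinded outcome data are analysed, delete the imbalance trigger and name one primary analysis. Either option closes the gap.

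**(a)** Keep the t-test that Section I powered as the sole primary result, and label every ANCOVA as a sensitivity analysis. This costs nothing.

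**(b)** Pre-specify an ANCOVA of 12-month muscle mass (or change) on treatment, visit-0 D₃-creatine muscle mass and sex. The t-test and adjustment for the other listed factors become sensitivity analyses. No new data are needed: sex is recorded for stratification, and the fasting instruction "on the day prior to these urine collections on visits 0 and 12 months" confirms that the baseline measurement is planned. The cost is two degrees of freedom. If neither covariate is prognostic, power falls by 2 to 4 points and the detectable difference rises from 2.20 to 2.27–2.33 kg, so Section I's target of less than 2.28 kg could be slightly missed. The model gains power once the covariates' multiple correlation with change exceeds about 0.24–0.32, a value that the documents do not give.

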Anamorelin has potential favorable effects on bone. Pulsatile GH secretion declines with aging and this likely contributes to bone loss and fracture risk. GH stimulation could counter bone loss as it stimulates osteoblast proliferation and differentiation *in vitro* (30). The effect of anamorelin on bone turnover or other bone parameters has not been reported, but treatment with another ghrelin receptor agonist, MK-669, for 9 weeks significantly increased the bone formation markers, serum osteocalcin by 29% and bone-specific alkaline phosphatase by 10.4%, and it also increased urinary N-telopeptide by 22.6% in functionally impaired older adults (30).

Anamorelin may be more effective on muscle than exogenous GH or IGF-1. Anamorelin stimulates the release of GH in its normal pulsatile pattern. Pulsatile GH affects muscle through increases in circulating and intramuscular IGF-1 (31). Circulating IGF-1, which is largely of liver origin, stimulates muscle protein synthesis by binding to IGF-1 receptors on myocytes and activating the mTOR pathway (31). In addition to increasing circulating levels of IGF-1, GH binds to its receptors on myocytes to stimulate the production of intramuscular

IGF-1 which acts locally to inhibit myostatin and promote satellite cell (myocyte) activity (32). Exogenous nonpulsatile GH treatment increases lean mass (33) but its use is limited by side effects (edema, arthralgias, paresthesias) that have not been seen in the anamorelin trials. Exogenous recombinant human (rh) IGF-1, unlike anamorelin, has no impact on intramuscular IGF-1 production.

Objectives and endpoints

Our central hypothesis is that anamorelin will increase muscle mass. We will also assess the secondary and exploratory outcomes described below in OS adults. To test this hypothesis, we will conduct a double-blind, 2-armed, parallel-group intervention trial in men and postmenopausal women age 50 and older with OS. Participants will be randomly assigned in a one to one ratio to: anamorelin or placebo and treated for 12 mo.

Specific aims

1. Primary aim To determine and compare the effects of anamorelin vs placebo on muscle mass by D₃-creatine dilution in OS adults. *Hypothesis: Anamorelin will increase muscle mass.*

2. Secondary aims

2A. To determine and compare the effects of anamorelin vs placebo on serum procollagen 1 intact N-terminal (P1NP), a biochemical marker of bone formation. *Hypothesis: Anamorelin will increase P1NP.*

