ECGs before and 1 & 4 hr post dose		X					^e DXA total body scans at 2, 6, &12 mo; spine and non-dominant hip scans at 12 mo (screening scans will serve as baseline)
Diet assessment ^a		X				X	^f Serum P1NP at 0, 2, 6, and 12 mo; serum IGF-1 and CTX at 0 and 12 mo; serum 25(OH)D at 0 and mo 6; and alpha-acid glycoprotein at visit 0; archive 4 aliquots serum and 1 of plasma at 0 and 12 mo.
Questionnaires ^b		X		X		X	^g Safety monitoring: fasting plasma glucose & serum AST/ALT at 0, 2, 6, and 12 mo; symptoms and other AEs documented
Muscle strength ^c	X	X	X	X		X	^h By pill diary and counting returned pills
Muscle perform. ^d		X	X	X		X	ⁱ Administer 60-mg oral dose of D ₃ -creatine
DXA scans ^e			X	X		X	^j Collect fasting spot urine for D ₃ -creatine dilution determination
Study blood ^f		X	X	X		X	
Dispense pills		X	X	X			
Safety measures ^g		X	X	X		X	
Adherence ^h			X	X		X	
D ₃ -creatine dosing ⁱ	X				X		
Fasting spot urine ^j		X				X	
Waist circumference						X	

In addition to the above study visits, we will contact participants by telephone at 4, 8, and 10 months to determine whether they have any study related concerns and to remind them of the importance of taking one study pill per day. The content of these calls will be documented on the Call/comment Log.

C. Inclusion and exclusion criteria

Inclusion criteria: Ability to sign informed consent form; community dwelling men (who are sterile or agree to use contraception throughout the study) and postmenopausal women (no menses for 5 years; early postmenopausal women are ineligible because their bone turnover rate is changing rapidly); age 50 years and older; sarcopenia defined as maximum grip strength <35.5 kg (men) and <20 kg (women) in either hand (excluding hands with severe pain or recent surgery) and/or gait speed <0.8 m/sec (11); osteopenia defined as spine (at L1, L2, L3, or L4) or non-dominant total hip or femoral neck BMD T-score between -1.0 and -2.5; mini-mental state examination (MMSE) score >21.

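### The secondary analysis names only a test of linear change over time and states no anamorelin-versus-placebo contrast for P1NP, appendicular lean mass or total lean mass

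*Combined protocol and SAP*

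**What the plan says.** In section J (Data analysis), the Secondary aims paragraph refers to the four measurements at baseline, 2, 6 and 12 months and continues: "we will test whether the change over time is linear with use of linear models with random effects". It adds that the observed ALM pattern will indicate possible long-term benefit, sets a 0.05 significance level, and labels secondary and exploratory findings hypothesis-generating. It names no treatment term, treatment-by-time term or group difference at any visit, and it does not mention P1NP or total lean mass.

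The primary aim is handled differently: "The change in muscle mass over 12 months will be compared between the intervention and control groups", by a two-sample t-test, with ANCOVA if the groups are imbalanced on listed factors. That wording covers muscle mass only.

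Other sections expect a group comparison for the secondary outcomes:

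- Specific aims 2A (P1NP) and 2D (appendicular and total lean mass) are each to determine and compare the effects of anamorelin and placebo.
- Section A (Study design) describes a test of anamorelin against placebo on 12-month changes in the primary, secondary and exploratory endpoints.
- Section I (Study power, Aim 2) calls P1NP the key secondary endpoint and says "statistical power is 82% to detect a difference of 0.32 nmol/L between placebo" and treatment, with 12 completers per group.

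**The concern.** A linearity test asks whether the time course is straight. It does not ask whether the arms differ, and it yields no treatment difference or confidence interval. Followed as written, the paragraph would leave aims 2A and 2D unanswered. It would do so in the very case the plan assumes for lean mass: section I projects the 3-month appendicular lean mass differences to 12 months and says "A linear rate of change is reasonable since in the safety extension of these original trials" weight continued to respond out to 6 months.

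At stake is the output a pilot most needs from its secondary endpoints, namely a treatment difference with its interval to guide a larger trial. With the contrast unwritten, the model terms and covariates for that estimate could be settled after the data are seen.

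**Working it through.** **Inputs**

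- P1NP difference 0.32 nmol/L and 12 completers per arm (section I, Aim 2).
- SD of change: "Standard deviation of 84-day change in P1NP was 0.267 nmol/L in all three treatment groups".
- Alpha 0.05 (section J). Sidedness is not stated, so two-sided is assumed.
- P1NP visits at 0, 2, 6 and 12 months (section B, footnote f).

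**1. Reproduce the plan's P1NP power as a two-group test of change**

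- Standard error = SD × √(2/n) = 0.267 × √(2/12) = 0.1090 nmol/L.
- Standardised effect = 0.32 / 0.1090 = 2.936.
- Normal approximation: Φ(2.936 − 1.960) = Φ(0.976) = 83.5%.
- Noncentral t, 22 df, critical value 2.074: 80.1%.
- One-sided versions give 90.2% and 88.5% and do not fit.

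The stated 82% lies between the two-sided figures. The power section therefore describes a two-sided, two-group comparison of change, which section J never writes down for P1NP.

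**2. What a linearity test sees when the drug effect is linear**

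With visits at 0, 2, 6 and 12 months, the quadratic departure from a straight line has weights (9, −3, −13, 7).

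- They sum to zero: 9 − 3 − 13 + 7 = 0.
- They are orthogonal to time: 9×0 − 3×2 − 13×6 + 7×12 = −6 − 78 + 84 = 0.
- A drug effect rising linearly to 0.32 at 12 months is 0, 0.0533, 0.16, 0.32 at the four visits. Its contribution is −3×0.0533 − 13×0.16 + 7×0.32 = −0.16 − 2.08 + 2.24 = 0.

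The drug effect cancels exactly, whatever its size and whatever the SD. The result therefore also covers ALM and total lean mass, for which the documents give no SD of change.

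**3. Simulated rejection rates under that linear effect**

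Settings: 12 per arm, independent visit errors with SD 0.267/√2 = 0.189, so that the SD of change is 0.267.

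| Test | Rejection rate |
|---|---|
| Quadratic contrast per participant, arms pooled | 5.1% |
| Quadratic term, no treatment term in the model (70 error df) | 3.5% |
| Two-df departure from linearity, no treatment term (69 error df) | 3.2% |
| Linearity test with arm-by-visit terms in the model (66 error df) | 4.9% |
| Two-group t-test of 12-month change | 80.1% |

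The values near 3% arise because the omitted arm difference inflates the residual error. No version of the linearity test exceeds about 5%. With no drug effect at all, the first and last rows give 4.9% and 5.1%, so the pooled linearity test cannot tell a linear drug effect from none.

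**4. Cost of the adjusted comparison**

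An ANCOVA with intercept, treatment, baseline value and sex has 24 − 4 = 20 error df, against 24 − 2 = 22 for the t-test. The critical value moves from 2.074 to 2.086.

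**The case against.** The strongest reply is that the comparison is already implied, and much of that stands. The aims say compare, section A fixes 12 months, and section I powers P1NP against placebo. The exploratory wording points the same way. It says "Exploratory outcomes will be analyzed as described above", and only then adds, for outcomes with more than two measurements, that the pattern of change is analysed as for ALM. Footnote f lists "serum IGF-1 and CTX at 0 and 12 mo". With two measurements, linearity cannot be tested, so for those markers the cross-reference must mean the primary t-test or ANCOVA. This suggests that the linearity work was meant to accompany a group comparison. It still does not place that comparison in the secondary paragraph or say which model and covariates it uses.

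A second reply is that a random-effects model can carry a treatment-by-time term. It can. Under the same simulation assumptions, a test of that slope difference rejects about 86% of the time when the drug effect is linear. But that is a different test from the one named, and the text is silent on model terms.

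Third, secondary results are for hypothesis generation, and summary statistics are planned at each time point. Both are true and limit the consequence. Summaries of each outcome do not supply a treatment difference with its interval.

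A reader might also infer that the linearity test would produce near-certain false positives. It rejects in 98% or more of simulated trials if both arms rise by 0.32 nmol/L by 2 months and stay there. The documents do not support using that figure. Nothing in them suggests such a rise on placebo, and it requires a model with no treatment term. With the quadratic compared between arms, the rate is about 5%.

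**Conclusion.** The point holds as a gap between the stated aims and the stated test. Section J gives no treatment contrast for P1NP, ALM or total lean mass, and the test it does name has only about its nominal 5% rejection rate when the drug effect is linear. A two-group test of 12-month P1NP change has about 80% power.

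The 5% result is algebraic and needs no SD. The 80% assumes 12 completers per arm, a two-sided 5% test, and the 84-day SD carried to 12 months.

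Three stronger readings are not supported. A reader might infer that no group comparison is planned; the aims, design and power sections make it probable that one is. A reader might infer that the time point is open; section A says 12 months. A reader might infer that the P1NP power is wrong; it reproduces. The primary analysis is untouched. The change should be made, but the trial's main conclusion does not depend on it.

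**What to change.** In section J, Secondary aims, name the anamorelin-minus-placebo difference in 12-month change, with its 95% CI, as the estimate for P1NP, ALM and total lean mass (aims 2A and 2D). Adjust for the baseline value and for sex, which is the randomisation stratum in section G. Obtain the estimate in one of two ways, and state which:

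- a 12-month ANCOVA; or
- the already planned random-effects model with treatment, visit and treatment-by-visit terms, reading off the 12-month contrast.

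Keep the linearity test as a description of the time pattern, and keep the hypothesis-generating label.

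The cost is a sentence or two of plan text and minor extra analysis. In the ANCOVA form, two error degrees of freedom are spent. No visits, samples or participants are added. The wording should be settled before the treatment groups are compared.

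### The primary t-test assumes equal variances, and the only stated remedy, a transformation, neither repairs unequal variances nor keeps the kg difference; Welch's test from the outset would do both at almost no cost

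*Combined protocol and SAP*

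**What the plan says.** Section J, primary aim, states that 12-month change in muscle mass "will be compared between the intervention and control groups with a two-sample Student's t-test". Student's test in this form pools the two arms' variances. If the groups are imbalanced on sex, age, physical performance, physical activity or protein intake, "we will adjust for those confounders within an ANCOVA model". That switch responds to imbalance, not to a failed model assumption.

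Further down, section J gives the remedy for failed assumptions: "Assumptions of normality and homoscedasticity will be evaluated in these models and appropriate variable transformations will be applied if needed to satisfy model assumptions". The transformation, the variable it applies to and the criterion for using it are not given. A second remedy follows, but for other models only: "If model assumptions do not hold for the linear mixed models, robust standard errors will be used". No unequal-variance, rank-based or resampling alternative is named for the primary test.

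Section I sizes the trial on the kg scale: SD of change 1.84 kg, expected placebo change -0.89 kg per year, expected difference 2.28 to 3.32 kg, and 12 per group to detect less than 2.28 kg. Section A plans 32 enrolled and 24 completers.

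**The concern.** Two features of the stated remedy make it a poor fit for the primary test.

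First, a transformation mainly treats skewness. If one arm's changes are more variable than the other's, for example because response to active drug differs between people, rescaling the outcome need not equalise the spread. The pooled standard error is then wrong whenever the arms also differ in size. Arm sizes may well differ at analysis: a quarter of those enrolled are expected to be lost, and D₃-creatine muscle mass is measured only at baseline and 12 months, so anyone lost before month 12 has no primary change value.

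Second, a transformation changes the quantity being estimated. A log ratio of the two masses tests a relative change; an asinh or cube root of the change tests a difference on a scale with no direct kg reading. Neither is the kg difference that section I powers and that a later trial would need for its own planning.

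The remedy also depends on a diagnostic with little power at this size. At the unequal splits examined below, Levene's test picks up a two-fold SD ratio in only 37 to 42% of simulated trials. And because the transformation is left open, it would be chosen after the data are seen; section G lists the study statistician among those not blinded.

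**Working it through.** **1. The plan's own figure.** Inputs from section I: SD 1.84 kg, 12 per group, target 2.28 kg. Assumed, because the plan does not state them for this calculation: two-sided test at 0.05 and 80% power.

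- Standard error of the difference: 1.84 × √(2/12) = 0.751 kg.
- Noncentrality: 2.28 / 0.751 = 3.04 on 22 degrees of freedom, giving 82.7% power.
- Detectable difference at 80% power: 2.20 kg with 12 per group, 2.31 kg with 11.

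So 12 per group is the smallest number that brings the detectable difference below 2.28 kg. The plan's figure reproduces, and it is a kg figure.

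**2. Can the outcome be transformed?** With normal changes and SD 1.84, the share below zero is Φ(0.89/1.84) = 69% on placebo. On anamorelin the mean would be -0.89 + 2.28 = 1.39 kg or -0.89 + 3.32 = 2.43 kg, giving 22% or 9% below zero. A plain log or square root of the change is therefore unavailable. A log ratio of the two positive masses, asinh, cube root and Yeo-Johnson are all available.

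**3. Why the pooled standard error goes wrong.** Let arm 1 have n₁ completers and r times the SD of arm 2. The pooled variance of the difference, relative to the true one, is on average

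[((n₁-1)r² + (n₂-1)) / (n₁+n₂-2)] × (1/n₁ + 1/n₂) / (r²/n₁ + 1/n₂).

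With r = 2:

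- 12 v 12: 1.00.
- 10 v 14: (49/22) × 0.1714 / 0.4714 = 0.81, so the standard error is about 10% too small.
- 9 v 15: (46/22) × 0.1778 / 0.5111 = 0.73, about 15% too small.
- 15 v 9 (larger SD in the larger arm): (64/22) × 0.1778 / 0.3778 = 1.37, about 17% too large.

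**4. Simulated two-sided error at nominal 5%** (normal data, 50,000 trials per row; splits and SD ratios assumed; arm 1 has the larger SD):

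| Completers, arm 1 v arm 2 | SD ratio | Student | Welch |
|---|---|---|---|
| 12 v 12 | 1.5 | 5.1% | 4.9% |
| 12 v 12 | 2 | 5.5% | 5.1% |
| 10 v 14 | 1.5 | 6.6% | 4.9% |
| 10 v 14 | 2 | 7.9% | 4.9% |
| 9 v 15 | 1.5 | 7.5% | 5.1% |
| 9 v 15 | 2 | 9.6% | 5.0% |
| 14 v 10 | 1.5 | 3.9% | 5.0% |
| 14 v 10 | 2 | 3.4% | 5.0% |
| 15 v 9 | 1.5 | 3.1% | 4.7% |
| 15 v 9 | 2 | 2.7% | 4.9% |

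Simulation error is about 0.1 point; repeat runs put the lowest Student figure at about 2.5%.

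**5. Does a transformation repair it?** A separate simulation used 100,000 null trials, SD ratio 2 and the larger SD in the smaller arm. Baseline muscle mass was assumed to be 22 kg with SD 3, since the documents give no baseline value.

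| Split | Student on kg | Log ratio | asinh | Cube root | Welch on kg |
|---|---|---|---|---|---|
| 10 v 14 | 8.1% | 8.1% | 7.6% | 7.5% | 5.1% |
| 9 v 15 | 9.6% | 9.8% | 8.5% | 8.2% | 5.1% |

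The log ratio changes nothing. The other two recover a small part of the excess.

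**6. What Welch costs.** At 12 v 12 with equal SDs of 1.84 and a true difference of 2.28 kg, simulated power is 82.4 to 82.5% for Welch against 82.7% for Student.

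**The case against.** The strongest reply is that the inflated figures need three things at once: unequal SDs, unequal completers, and the larger SD in the smaller arm. The plan gives one SD and 12 per group, and at 12 v 12 there is no material problem. If 32 enrol as 16 v 16 and the 8 losses fall at random, the chance that a given arm loses at least 6 is about 11%, and at least 7 about 2%. The gastrointestinal complaint rates quoted in the risk section (6% v 2%, and 2% v under 1%) do not point to a 7 v 1 loss, and section K keeps participants who stop pills in follow-up. With the larger SD in the larger arm, the pooled test is conservative. All of this stands, and it is why the point is minor. It does not defend the pooled test over Welch, because the error is off in one direction or the other whenever size and spread both differ, and the saving from pooling is about 0.3 points of power.

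A reader might infer that transformation cannot work on a signed change and that the primary test therefore has no usable fallback. The text does not support that. It limits neither the type of transformation nor the variable, and several accept negative values. For skewed data with equal variances such a step can help: in a skewed example with 24 values, Yeo-Johnson cut rejections of normality from 88% to 25%.

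A reader might also carry the point over to P1NP, CTX and IGF-1, arguing that they should be on the log scale from the start because section I calls "detecting a 25% group difference from placebo is clinically meaningful". That does not follow either. Section I sizes P1NP in absolute units (0.32 nmol/L, SD 0.267), and a power gain from logging depends on an assumed baseline variability. P1NP has four visits and falls under the mixed models, where robust errors are available. All three markers are positive, so the existing wording already permits logs. Section J treats these results as hypothesis-generating.

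**Conclusion.** The concern holds as a minor one with a cheap improvement. For the primary t-test, transformation is the only stated remedy; it does not deal with unequal variances, and it moves the analysis off the kg difference used for planning. Under assumed SD ratios of 1.5 to 2 and completer splits of 10 v 14 or 9 v 15, the pooled test's two-sided error lies between about 6.6 and 9.6% in one direction and about 2.5 and 3.9% in the other, with Welch near 5% throughout.

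It should not be read as showing that the trial's error rate is inflated. In the planned 12 v 12 case it is nearly nominal, and the documents give no evidence that the SDs or completer numbers will differ. The 12 per group reproduces and is unaffected. The size rests on the assumed SD ratios, the assumed splits, normal data and a two-sided test; the transformation results also rest on the assumed baseline mass.

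**What to change.** In section J, primary aim:

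1. Replace Student's t-test with Welch's t-test on 12-month change in kg, used from the outset rather than after a variance check. If the ANCOVA is used, give it heteroscedasticity-consistent standard errors in a form suited to small samples.
2. State that the primary outcome stays on the kg scale whatever the diagnostics show, and that any transformed analysis is a sensitivity analysis only.

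A permutation test of the mean difference should not be added as the safeguard: it is not valid when variances and arm sizes both differ, which is the case at issue.

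The cost is a change of wording and about 0.3 points of power at 12 v 12 with equal SDs. Sample size, visits and data collection are unchanged.
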